### **6.2.5 Blinding**

Patients and all study staff will be blinded to treatment assignment. Study drug or placebo doses for infusion will be prepared by the pharmacist or qualified site staff in a blinded manner.

Investigators will have direct access to unblinding of treatment through the IWRS in the event of an emergency in which knowledge of treatment assignment would aid in immediate patient care. Should a patient's treatment be unblinded, every effort will be undertaken to protect the blind within the study team. Only a pre-specified group of unblinded team members (safety associate, data manager, biostatistician) will have access to the patient's unblinded data while the study is ongoing.

### **6.2.6 Concomitant medications**

Patients will refrain from participation in any other investigational study drug trial in which receipt of any investigational drug occurred within 5 half-lives or 30 days, whichever is longer, prior to Day 0 and during the entire study.

Treatment with rituximab monotherapy or rituximab combination therapies (eg, with bendamustine, fludarabine, ibrutinib, or cytotoxic drugs) is prohibited.

During Part A, patients will not take any prescription or over-the-counter medications/products until completion of the follow-up assessments, unless prescribed by the Investigator or another physician for the treatment of an AE.

As noted in [Section 5.2](#), concurrent administration of erythropoietin and/or a daily dose of corticosteroids (equivalent to  $\leq 10$  mg/day of prednisone) is acceptable provided the patient has been on a stable dose during the previous 3 months; concurrent use of B12, folate and iron supplementation is acceptable provided the patient has been on a stable dose during the previous 4 weeks.

Topical therapies without risk of systemic absorption may be allowed, and non-prescription medications for treatment of minor intercurrent illnesses (headache, viral upper respiratory tract infections, etc) are permitted at the discretion of the PI. Hormonal contraception in female patients is allowed provided patients are receiving stable treatment  $\geq 3$  months prior to Screening. Any medication taken by the patient during the study, along with its strength, frequency of dosing, and reason for its use, will be documented in the patient's source data and the eCRF.

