CAGD is an autoimmune hemolytic anemia caused by IgM-induced CP activation. The IgM autoantibodies in CAGD are referred to as “cold agglutinins” given their inherent property of increased binding as a function of decreased temperature. The cold agglutinin thermal amplitude, which is the highest temperature at which the cold agglutinin can be detected to react with the red blood cell antigen approaches core body temperature in many patients (1). CAGD symptoms are typically triggered by exposure to cold environmental temperatures (ie, temperatures at or below core body temperature), viral infections, or inflammation (2, 3, 4, 5, 6, 7). All patients with CAGD have active disease with varying levels of chronic, ongoing hemolysis resulting in anemia (8). CAGD patients without recent transfusion remain significantly compromised with symptoms associated with hemolytic anemia including shortness of breath, fatigue, lightheadedness, and general weakness, in addition to vascular symptoms such as Raynaud’s and acrocyanosis. The symptomatic impact of anemia is increased in CAGD patients due to the advanced age of the population (1, 9) who tolerate anemia symptoms poorly. CAGD patients who have not recently been transfused often have similar Hgb levels as recently-transfused patients and can have significant symptoms (9). These complications have a significant adverse impact on quality of life. Patients with CAGD are also at increased risk of arterial and venous thromboembolic events, including potentially life-threatening events such as stroke, myocardial infarction, and pulmonary embolism (10, 11, 12). This increased risk of thromboembolic events occurs in CAGD patients with even mild anemia and is related to the ongoing hemolysis (10, 12). Thus, CAGD patients who are not recently transfused remain at risk for severe complications of the disease.

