### 4.3.3 Exploratory efficacy endpoints (Part A)

- Mean change from baseline in QOL, as assessed by the change in the five level EuroQol – five dimensions questionnaire (EQ-5D-5L) scores at the treatment assessment endpoint
- Mean change from baseline in QOL, as assessed by the change in the 12-Item Short Form Survey (SF-12®) at the end of treatment assessment endpoint
- Proportion of patients with  $\geq 12$  g/dL Hgb at treatment assessment endpoint
- Incidence of thromboembolic events after the first 5 weeks of study drug administration
- Median time to normalization of bilirubin
- Median time to normalization of LDH
- Median time to normalization of haptoglobin
- Median time to Hgb of  $\geq 12$  g/dL
- Proportion of patients normalizing haptoglobin at treatment assessment endpoint

- Proportion of patients normalizing bilirubin at treatment assessment endpoint
- Proportion of patients with abnormal LDH at baseline who normalize LDH at treatment assessment endpoint
- Patient's Global Impression of Change (PGIC) to assess the patient's perception of changes in CAgD disease burden at EOT
- Patient's Global Impression of [Fatigue] Severity (PGIS) to assess the patient's perception of changes in fatigue at EOT
- Incidence of disabling circulatory symptoms at treatment assessment endpoint
- Total healthcare resource utilization at EOT

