### 5.1 INCLUSION CRITERIA

All patients must meet all the following inclusion criteria to be enrolled:

- I 01. Adult male and female patients  $\geq 18$  years of age at Screening.
- I 02. Body weight of  $\geq 39$  kg at Screening.
- I 03. Confirmed diagnosis of primary CAgD based on the following criteria:
  - a) Chronic hemolysis
  - b) Polyspecific direct antiglobulin test (DAT) positive
  - c) Monospecific DAT strongly positive for C3d
  - d) Cold agglutinin titer  $\geq 64$  at  $4^{\circ}\text{C}$
  - e) IgG DAT  $\leq 1+$ , and
  - f) No overt malignant disease
- I 04. Hemoglobin level  $\leq 10.0$  g/dL.
- I 05. Bilirubin level above the normal reference range, including patients with Gilbert's Syndrome.
- I 06. Ferritin levels above the lower limit of normal. Concurrent treatment with iron supplementation is permitted if the patient has been on a stable dose during the previous 4 weeks.
- I 07. Presence of one or more of the following CAgD-related signs or symptoms within 3 months of Screening:
  - a) Symptomatic anemia defined as:
    - i. Fatigue
    - ii. Weakness
    - iii. Shortness of breath
    - iv. Palpitations, fast heart beat
    - v. Light headedness and/or
    - vi. Chest pain
  - b) Acrocyanosis
  - c) Raynaud's syndrome

- d) Hemoglobinuria
  - e) Disabling circulatory symptoms, and/or
  - f) Major adverse vascular event (including thrombosis)
- I 08. Bone marrow biopsy within 6 months of Screening with no overt evidence of lymphoproliferative disease or other hematological malignancy. An additional bone marrow biopsy will be required if the prior bone marrow is deemed unsuitable for analysis by the Sponsor.
- I 09. Documented vaccinations against encapsulated bacterial pathogens (*Neisseria meningitidis*, including serogroup B *meningococcus*, *Haemophilus influenzae*, where available, and *Streptococcus pneumoniae*) within 5 years of enrollment or as specified in [Section 6.1.1.1](#).
- I 10. Patients must be willing to receive transfusions if they meet the eligibility criteria during the study treatment period. Patients who do not have a recent history of transfusion due to patient refusal or patient decision should not be enrolled if they do not agree to receive blood transfusions as needed.
- I 11. Adequate IV access.

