### **5.3 REMOVAL OF PATIENTS FROM STUDY PARTICIPATION, AND STUDY SUSPENSION AND STOPPING RULES**

Patients will be informed that they are free to withdraw from the study at any time and for any reason. Patients should inform the site of withdrawal in writing. The Investigator (or designee) may remove a patient from the study if, in the Investigator's (or designee's) opinion, it is not in the best interest of the patient to continue the study. Patients may be withdrawn due to the following:

- Change in compliance with inclusion/exclusion criteria that is clinically relevant and affects patient safety
- Occurrence of AEs that, in the opinion of the Investigator, may jeopardize patient safety or data integrity. This includes clinically significant hematologic breakthrough events attributable to the development of ADA and/or the development of positive SLE auto-antibody titers
- Occurrence of pregnancy in patient while receiving study drug
- Intake of non-permitted concomitant medication that might affect patient safety or study assessments/objectives
- Clinical signs of SLE or any other immune complex disease
- Hypersensitivity or allergic reaction, including anaphylaxis, to study drug

The Investigator will immediately notify the Sponsor's Study Monitor of all patients who withdraw from treatment. In case of withdrawal, all ET assessments should be performed as applicable (Section 6.1.4). The date the patient is withdrawn from the study and the reason for withdrawal will be recorded on the patient's electronic Case Report Form (eCRF). All withdrawn patients will be followed until resolution of all their AEs or until the unresolved AEs are judged by the Investigator (or designee) to have stabilized. Patients who withdraw from study early (prior to Week 5) may be replaced at the discretion of the Sponsor. Patients who withdraw from the after Week 5 and prior to Week 23 will not be eligible to participate in Part B.

The entire study may be discontinued at the discretion of the Sponsor based on the occurrence of the following:

- Adverse events unknown to date or increased frequency, and/or severity, and/or duration of known AEs,
- Results of the interim analysis (Section 7.9) demonstrating absence of clinically significant increases in Hgb,
- Medical or ethical reasons affecting the continued performance of the study,
- Difficulties in the recruitment of patients,
- Cancellation of or change in drug development program per the discretion of the Sponsor.

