### 6.1.3 Weeks 1-25 Part-A

On Days 7, 21, 35, 49, 63, 77, 91, 105, 119, 133, 147, 161, and 175, patients will undergo the following procedures before administration of the study drug:

- Serum or urine pregnancy test in WOCBP (ie, women of child bearing potential), if applicable, on Days 21, 49, 77, 105, 133, and 161
- Physical examination (brief)
- Vital signs
- Hematology panel
- Clinical chemistry panel
- Solicited symptomatic anemia assessment
- QOL assessments:
  - FACIT-Fatigue: all scheduled visits
  - PGIS: Days 35, 77, and 119 only
  - PGIC: Days 35, 77, and 119 only
  - SF-12: Days 35, 77, and 119 only
  - EQ-5D-5L: Days 49, 91, and 133 only
- 12-lead ECG (Day 91 only)
- During Part A, ADA samples will be collected at predose on Day 0, 7, 35, 77, 133, 175 on Day 182 (EOT)
- PK and PD sampling
- Disease-related biomarkers (subset at Day 91 only); refer to the Laboratory Manual for details
- Record healthcare resource utilization data since previous assessment on Days 21, 49, 77, 105, 133, and 161
- Record concomitant medications/procedures including transfusions
- Adverse event monitoring

At 0 hour, study drug will be infused via an indwelling IV catheter over a period of 60 ±5 minutes. Patients with underlying cardiopulmonary disease may receive a 2-hour infusion with Sponsor approval. Additionally, study drug infusion may be interrupted or slowed in the event of suspicion of an allergic reaction or anaphylaxis.

After completion of the infusion, patients will undergo the following procedures:

- Vital signs at 1 hour (±5 minutes) postdose
- 12-lead ECG (Day 91 only) at 1 hour (±15 minutes) postdose
- PK and PD sampling at 1 hour (±15 minutes) postdose

Vaccinations should be administered according to [Section 6.1.1.1](#), if applicable, or [Appendix I](#) for Japan.

Note: Patients who miss a dose (ie, outside the dosing window or >17 days since last dose) should return to the site for an unscheduled visit 1 week prior to the next scheduled dose in order to receive an additional loading dose. The patient should then resume subsequent dosing visits every 14 days after the loading dose.

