4.3.4 Subgroup analyses

Definitions of subgroups

The following subgroups will be considered for the selected analyses:

- Age (<65 , ≥ 65)
- Gender (Female, Male)
- Baseline weight (<75 kg, ≥ 75 kg)

- Baseline Hgb level (<median, >= median g/dL)
- Previous rituximab monotherapy use (Yes, No)
- Previous rituximab monotherapy or rituximab and other cytotoxic therapy use (Yes, No)
- Prior thromboembolic events within the last 1 year (Yes, No)
- Previous reculizumab use (Yes, No)

In case of very few subjects (eg, <5) in a category, the cutoff value may be changed to suit the distribution of these factors.

Analysis Methods

The CMH odds ratio and 95% CI will be summarized for the subgroups defined above. As with the primary endpoint, the odds ratios for each subgroup will be stratified by baseline hemoglobin (< median baseline Hgb vs \geq median baseline Hgb) and geographic region (Japan/Australia, United States, Europe). The CMH test may not be stratified in the case of completely unbalanced strata. The consistency of the odds ratio among these sub-populations will be examined by forest plots.

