5.3 APPENDIX 3 DEMOGRAPHICS AND BASELINE CHARACTERISTICS, PRIOR OR CONCOMITANT MEDICATIONS

Demographics and baseline disease characteristics will be summarized for the FAS.

Demography

Demographic characteristics including age (years), age category (<65, ≥65), gender, race, ethnicity, country, geographic location, height (cm), weight (kg), weight category (<75 kg, ≥75 kg), and body mass index (kg/m²) will be summarized. Geographic locations are defined as Europe, North America, Asia/Japan, and other.

General Medical History

Medical history by system organ class (SOC) and preferred term (PT) will be summarized. A subject will be counted only once if they reported one or more occurrences in the same SOC or PT.

A summary of prior hospitalizations related to CAD within the last 2 years, prior hematological malignancies within the last 5 years, prior non-malignant hematologic diseases within the last 5 years, and prior thromboembolic events within the last 1 year will be presented based off the “Targeted Medical History” eCRF form.

Baseline Disease Characteristics

Screening and baseline lab parameters, including hematology (such as Hgb, bilirubin, LDH), Gilbert’s Syndrome testing, and bone marrow biopsy results will be summarized. Prior transfusion history (eg, number of transfusions within 12 months of study entry) will also be summarized.

Severity of anemia symptoms and other CAD-related disease characteristics (eg, presence of acrocyanosis, Raynaud’s syndrome, hemoglobinuria, disabling circulatory symptoms, and major adverse vascular events) within 3 months of screening will be summarized.

The proportion of subjects who had documented vaccines within 5 years and who have received vaccination during the study will be summarized. The vaccines include meningococcal vaccine, S. pneumoniae vaccine, and H. influenza vaccine.

Prior or concomitant medications

Prior medications are those taken before the first dose of study drug in Part A. Concomitant medications are those administered on or after the first dose of study drug, or those administered before the first dose that are ongoing when study treatment begins. Prior and concomitant medications will be coded using World Health Organization drug enhanced dictionary (March 2020 version or higher).

Separate tables will be generated to summarize concomitant medications and concomitant protocol-prohibited medications by ATC level 2 and WHODrug standardized medication text.

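### Read literally, Protocol 6.2.6 bars background anticoagulant, antiplatelet and cardiac medicines in Part A for patients whom the eligibility criteria admit

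*Protocol*

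**What the plan says.** Protocol 6.2.6 sets the general rule: "During Part A, patients will not take any prescription or over-the-counter medications/products until completion of the follow-up assessments". It then lists exceptions: physician-prescribed treatment of an adverse event; erythropoietin, low-dose corticosteroid, B12, folate and iron, each on a stable dose; topicals that are not absorbed; non-prescription products for minor illness; and established hormonal contraception. Protocol 4.1 names 6.2.6 as the place where excluded and allowed medicines are listed, so this is the operative list. The section closes by requiring any medication taken to be documented.

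The population is described elsewhere. Criterion I 07 f in Protocol 5.1 makes a major adverse vascular event, thrombosis included, within 3 months of Screening one of six qualifying signs. Protocol 2.2 states: "Patients with CAGD are also at increased risk of arterial and venous thromboembolic events". Protocol 6.1.2 and 6.1.3 add: "Patients with underlying cardiopulmonary disease may receive a 2-hour infusion with Sponsor approval". SAP 4.3.4 plans a subgroup defined by thromboembolic events in the year before the study.

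On handling, Protocol 5.3 lists this among the reasons why a patient may be withdrawn: "Intake of non-permitted concomitant medication that might affect patient safety or study assessments/objectives". SAP Appendix 3 (5.3) counts as concomitant "those administered before the first dose that are ongoing when study treatment begins".

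**The concern.** The protocol admits patients with a recent thrombosis or cardiopulmonary disease, then gives a medication rule under which they could not go on taking the usual treatment for those conditions. A site that follows the sentence exactly would stop an anticoagulant or cardiac medicine in a population that the protocol itself describes as being at raised thromboembolic risk. Thromboembolic events are a safety endpoint (Protocol 4.3.5) and also an exploratory one: "Incidence of thromboembolic events after the first 5 weeks of study drug administration".

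A site that uses clinical judgement instead departs from a written rule. Sites may then differ in whether they log a deviation, and in how they answer the eCRF question on prohibited medication at each visit. The withdrawal ground in Protocol 5.3 could also be reached: the coagulation panel in Appendix A includes PT-INR and aPTT, so an anticoagulant could be said to affect a study assessment.

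**Working it through.** There is no planned figure to reproduce. The check compares the text of the rule with the rest of the documents, with a little arithmetic on duration.

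1. **The exceptions in Protocol 6.2.6, one by one.**

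| No. | Permitted | Condition | Covers a background anticoagulant, antiplatelet or cardiac medicine? |
|---|---|---|---|
| 1 | Treatment of an adverse event | Prescribed by a physician | No (see step 2) |
| 2 | Erythropoietin | Stable 3 months | No |
| 3 | Corticosteroid | Up to 10 mg/day prednisone equivalent, stable 3 months | No |
| 4 | B12 | Stable 4 weeks | No |
| 5 | Folate | Stable 4 weeks | No |
| 6 | Iron | Stable 4 weeks | No |
| 7 | Topicals | No risk of systemic absorption | No |
| 8 | Non-prescription products for minor illness | PI discretion | No |
| 9 | Hormonal contraception | Stable at least 3 months before Screening | No |

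Result: 0 of 9.

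2. **Does the adverse-event exception close the gap?** Adverse events are collected from consent (Protocol 6.7), and thromboembolic events before study entry are medical history (SAP 4.1). Treatment of a thrombosis that occurs after consent is therefore allowed. Continued treatment of one that occurred before consent is not.

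3. **Is there a permission elsewhere?** None was found in the eligibility criteria, the withdrawal rules, the visit instructions or the SAP. Exclusion E 11 lets the investigator keep out patients whose illness endangers them or the data, but it permits no medicine. The documentation requirement in 6.2.6 and the SAP definition of concomitant medication are recording and reporting rules. They show that ongoing medicines were foreseen, but they do not authorise any.

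4. **How long the ban lasts, on the nominal schedule.**
   - Patient who enters Part B, counted from Day 0: 182 / 7 = 26 weeks.
   - The same patient if Screening is counted as Part A, as the Duration of Treatment table in the Synopsis lists it: (42 + 182) / 7 = 32 weeks.
   - Patient who completes dosing but does not enter Part B, with follow-up 9 weeks after the last dose: Day 175 + 63 = Day 238, and 238 / 7 = 34 weeks from Day 0.

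5. **Would a stable-dose condition of the existing kind work?** Assume a full 6-week Screening, treatment started on the day of the thrombosis, 3 months taken as 13 weeks, and stability judged at Day 0. A qualifying event then lies between 6 and 6 + 13 = 19 weeks before Day 0. A 13-week stability rule would be met only if the event was at least 13 - 6 = 7 weeks before Screening. Later events, where treatment is most recent, would still be barred. The permission should therefore rest on a start before Day 0 and allow dose adjustment.

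6. **Does the primary endpoint move?** Protocol Table 2 refers only to treatment for CAgD. SAP 4.1 limits the prohibited list to rituximab, cytotoxic drugs and other investigational drugs, and has medical review reconcile it with the eCRF answer. SAP 4.2 removes patients from the per-protocol set, on medication grounds, only for prohibited CAD treatment. A background anticoagulant fits none of these.

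**The case against.** The best defence is that this is a drafting slip which the rest of the plan reads around. No section tells a site to stop or wash out anything. Medicines are recorded before dosing, and the SAP provides for those already under way. Withdrawal is optional and limited to medicines that matter for safety or assessments. Deviations are adjudicated medically and graded major or minor (SAP 4.2), which evens out uneven classification by sites. Recent thrombosis is one of six alternative qualifying signs, and nothing shows how many patients entered by it. Timing also counts: Version 8 is dated 4 November 2020, the first patient was randomized on 16 April 2018, the first entered Part B on 27 November 2018, and the July 2020 Part B SAP already describes Part A treatment in the past tense.

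Much of this stands. It makes actual harm less likely and reduces the number of patients an amendment could help. It does not supply a permission. Adjudication can grade only the deviations that sites log, and a rule that is safe only when sites disregard it should be corrected. The past-tense wording suggests that Part A was well advanced, but no document says that it had ended.

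**Conclusion.** The point holds as a gap in the Part A medication rule: the literal text bars medicines that some admitted patients can be expected to need, and no other section lifts the bar. Its consequences are patient safety and consistent classification of deviations. Its size in patients or events cannot be stated, because the documents give neither the number taking such medicines nor the number still in Part A.

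Three stronger readings are not supported:
- A reader might infer that the protocol orders anticoagulants to be stopped. It does not; stopping is only what exact compliance with one sentence would imply.
- A reader might infer that patients on background medicines become non-responders or bias the responder comparison. The endpoint definition and the SAP list are confined to CAgD therapies, so the effect is essentially nil, provided the planned reconciliation of the eCRF answers is carried out.
- A reader might infer that Part A vaccination is blocked. Protocol 6.1.1.1, 6.1.3 and Appendix I direct it expressly.

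The conclusion assumes that no manual outside these documents already grants the permission.

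**What to change.** Amend the general sentence itself. A permission added after an unchanged ban, with an exception for therapies prohibited in the section, would be circular. Suggested text:

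> In Part A, patients take no prescription or over-the-counter product until follow-up is complete, other than physician-prescribed treatment of an AE, the items listed below, and medicines for pre-existing conditions other than CAgD, or for prior vascular events (including anticoagulant, antiplatelet, cardiac and respiratory medicines), that were started before Day 0, which may continue and be dose-adjusted as clinically needed. This does not permit rituximab, cytotoxic drugs, other immunosuppressants, complement inhibitors or investigational drugs, or corticosteroids, erythropoietin, iron, B12 or folate outside their existing dose and stability limits.

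The second sentence is needed so that the permission does not let in drugs that could affect haemoglobin or hemolysis, such as a higher steroid dose given for a respiratory condition.

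Record the permitted medicines in the eCRF as concomitant, and neither as deviations nor as prohibited CAD medications. Leave the SAP 4.1 list as it is.

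The cost is a short passage in an amendment with ethics committee submission (Protocol 8.1) and a memo to sites. It needs no new data and changes no analysis. If no patient remains in Part A, drop the amendment and put the same classification in the deviation rules that SAP 4.2 requires before database lock.
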